^a = data collected during phone call (vs REDCap)

Phone Orientation Visit. Study personnel will call the participant at their scheduled session time and provide a detailed description of the study and obtain verbal consent. A copy of the informed consent and a PowerPoint describing the study in detail will be mailed and/or emailed to participants before the orientation session. If the participant decided to consent to the study, a series of self-report questionnaires to complete will be emailed to them (see Aim 3 below). Individuals who are ineligible or decline to participate will receive self-help materials and referrals for smoking cessation and alcohol use programs.

Zoom Orientation Visit. Consented participants will be scheduled for a group Zoom Orientation session one week before the first treatment session. Prior to the visit, participants will be provided a packet of instructions on how to access and navigate the video-conferencing app, Zoom, and additional materials related to the study (e.g. session handouts, welcome materials). Tablets, webcams, and/or microphones will be provided to participants on an as-needed basis. This orientation session will take place via Zoom. During this session, participants will be provided with a training on how to use video-conferencing app and will discuss the other relevant materials sent to participants in preparation for the first treatment visit. Prior to all Zoom visits in the study, participants will join a waiting room before they are admitted to the group, where they will see banners with reminders about sessions content, privacy standards, etc. This procedure will be followed for all treatment sessions as well as the Zoom Orientation session.

Randomization. Three stratification variables will be included: gender (men vs women), race/ethnicity (non-Hispanic White vs Other), and smoking rate (20+ cigarettes per day [CPD] vs less than 20). Within these 8 cells, eligible participants will be assigned to the two treatments using balanced-permuted block randomization with a block size of 4.

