To ensure participant confidentiality, no unique identifiers will be recorded into the dataset to be analyzed. Data will be collected via REDCap. The entered and reviewed data will be transferred monthly to a SPSS database.¹⁷⁴

Sample Size. Randomizing 64 participants to MBRP-SA and CBT will provide sufficient data for assessing feasibility of the RCT, based on existing recommendations in the literature for sample size estimates in feasibility studies.^{175,176} A full set of statistical analyses focusing on treatment differences will be performed as part of the feasibility assessment. However, the sample size will not be sufficient for detecting treatment differences for anything less than large effect sizes (e.g., Cohen's $d \geq .72$) for simple, two-group comparisons of a continuous variable with $\alpha=.05$, power $\geq .80$, and a two-tailed test. Binary variables assessed under the same testing conditions would require an $OR \geq 5.95$.

Data Analysis Overview. Analyses will be conducted with SPSS and SAS version 9.4¹⁷⁴ and Mplus Version 7.¹⁷⁷ Descriptive statistics of demographics, smoking history, and alcohol history variables will be calculated and group comparisons will be performed. Descriptive statistics of all study measures (i.e., proximal and distal measures of alcohol use and smoking) will be calculated. Although underpowered to detect small- or medium sized sex differences, all analyses will examine sex as a covariate. Furthermore, analyses will include treatment group (i.e., each subset of participants who are treated with MBRP-SA or CBT together) when the intraclass correlation coefficient is > 0.10 .

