Aim 2 - Evaluate benchmarks regarding feasibility and acceptability. Feasibility will be assessed by the multiple indices described in Table 5. Each index will either be compared to published norms (e.g., CSQ) or our prior experience with clinical trials. We expect to recruit adequate numbers of eligible participants during the study timeframe with efficient cost expenditures, retain at least 80% through the end of treatment, and retain at least 70% through the end of the study. Treatment acceptance and satisfaction are expected to be 80% or higher, and participants are expected to comply with treatment requirements. The team will determine whether corrective actions for future studies are needed when an index suggests underperformance. Evaluation of all indices will inform and guide modification prior to the proposal of a full-scale RCT.

Aim 3 - Collect and examine descriptive data on proximal and distal variables associated with alcohol use and smoking. Descriptive statistics of proximal measures (e.g., negative affect, self-efficacy) will be presented in figures to review change over time and treatment differences. Generalized estimating equations (GEE) will be used to fit population-averaged models with the main variables of treatment, time, and their interaction. An AR(1) working correlation matrix will be used with $r=.70$. Covariates and potential confounding variables will be included, as warranted. This approach preserves data for analysis by avoiding listwise deletion of observations when at least one dependent variable was observed. Qualitative analyses (e.g., thematic analysis) may also be conducted on aspects of the treatment process.

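### Race/ethnicity and smoking rate are stratification factors but are not pre-specified in the Aim 3 models; if they are prognostic, reported between-arm standard errors for continuous outcomes would be modestly too wide

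*Combined protocol and SAP*

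**What the plan says.** Under Aim 2, Randomization, the plan states: "Three stratification variables will be included: gender (men vs women), race/ethnicity (non-Hispanic White vs Other), and smoking rate", the last split at 20 cigarettes per day. This gives eight cells, within which "eligible participants will be assigned to the two treatments using balanced-permuted block randomization with a block size of 4".

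The analysis is in section G, Data Management and Statistical Considerations for Study 2. The Data Analysis Overview says "all analyses will examine sex as a covariate". The Aim 3 paragraph specifies GEE with "population-averaged models with the main variables of treatment, time, and their interaction", and then: "Covariates and potential confounding variables will be included, as warranted". The distal outcomes (heavy drinking and 7-day abstinence) are to be handled similarly, at weeks -4, 0, +3, +8 and +16, with an AR(1) working correlation of .60. Section 4 only points back to the aims.

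So sex is the one stratification factor named for the models. No passage commits race/ethnicity or smoking rate, and none rules them out.

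**The concern.** Stratified blocks make the arms nearly alike on the factors, so those factors contribute little to the chance difference between arms. A model that omits a prognostic factor leaves its variance in the residual, and the standard error is then computed as if the arms could have differed freely on it. The reported interval for a between-arm difference is too wide for the design that was run.

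There is a second issue that does not depend on prognostic strength. The covariate rule has no candidate list, criterion or timing. With 64 participants and several outcomes, the reported differences could depend on choices made after the data are seen.

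What is at stake is the Aim 3 output. The plan intends means, percentages and 95% confidence intervals to guide the sample size of a full-scale trial.

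**Working it through.** **The plan's own figures.** Inputs from the Sample Size paragraph: 64 randomised (32 per arm), alpha .05, "and a two-tailed test", power .80, d of at least .72, OR of at least 5.95. At d = .72 and 32 per arm, exact t power is .809, and the smallest d with 80% power is .711, so the stated d reproduces. The OR reproduces if a 10% control rate is assumed (10% vs 39.8%, power .802); the plan gives no control rate. Both figures are for simple two-group comparisons without covariates.

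**Analytic size, continuous outcome, one time point.** The prognostic strength is not in the documents. Assumption: the three factors jointly explain R2 of .05 to .20, in equal thirds. Sex is already in the model, so the ratio of the sex-only SE to the fully adjusted SE is sqrt((1 - R2_sex)/(1 - R2_total)).

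| R2 total | R2 sex | SE ratio | Equivalent participants, 64 x (1 - 1/ratio^2) |
|---|---|---|---|
| 0 | 0 | 1.000 | 0 |
| .05 | .0167 | sqrt(.9833/.95) = 1.017 | 2.2 |
| .10 | .0333 | sqrt(.9667/.90) = 1.036 | 4.4 |
| .20 | .0667 | sqrt(.9333/.80) = 1.080 | 9.1 |

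In terms of detectable d (ignoring the two degrees of freedom), at R2 = .20 the move is from .711 x sqrt(.9333) = .687 to .711 x sqrt(.80) = .636. At R2 = .05 it is from .705 to .693.

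**Simulation of the planned model.** About 2,000 trials per setting with no true effect: N = 64, eight strata, blocks of four, five time points, AR(1) fixed at .60, sex in both models, no dropout. Assumed prevalences were 50%, 35% and 40% for the gender, race/ethnicity and smoking-rate indicators. R2 here is for the two omitted factors only. Results for the week-16 between-arm contrast, continuous outcome, robust SE:

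| R2 (two factors) | SE, sex only | SE, all three | Ratio | Sampling SD, sex only / all three | Null rejection, sex only / all three |
|---|---|---|---|---|---|
| 0 | .244 | .242 | 1.01 | .263 / .263 | .075 / .077 |
| .04 | .249 | .242 | 1.03 | .252 / .251 | .060 / .066 |
| .11 | .259 | .243 | 1.07 | .252 / .251 | .048 / .062 |
| .24 | .281 | .243 | 1.16 | .265 / .260 | .038 / .073 |

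The direction agrees with the formula. The sampling SD barely moves (Monte Carlo error about .004), so the estimator already has the precision and only the reported SE fails to show it. The uncorrected robust SE also runs low at this sample size: with all three factors at R2 = .11 it is .243 against a sampling SD of .251.

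**Treatment-by-time contrast (week 16 vs pre-treatment), same runs.** The robust SE is unchanged by the two factors: .323 vs .323 at R2 = .11, and .324 vs .324 at .24. A model-based SE does fall, from .377 to .327 at R2 = .24. The plan does not say which type will be used.

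**Binary outcome, logit scale, week 16.** Adding the factors raises the robust SE of the log-OR: .571 to .587 for moderately prognostic factors and .557 to .606 for strong ones.

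**Clustering, for scale.** Therapy groups have 8 to 10 members, and group enters the model only if the ICC exceeds 0.10. The design effect 1 + (m - 1) x ICC runs from 1 + 7 x .05 = 1.35 to 1 + 9 x .10 = 1.90 (ICC range assumed). Ignoring it makes the SE too small by 1 - 1/sqrt(1.35) = 14% to 1 - 1/sqrt(1.90) = 27%.

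**The case against.** The strongest reply is that nothing is excluded: the covariate clause allows both factors in. The effect depends on a prognostic strength that the plan does not give, and Study 2's primary outcomes are the Table 5 benchmarks, which these models do not touch. All of that stands. It limits the size and priority of the point but does not supply the missing commitment.

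A reader might infer several stronger things that the documents do not support:

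- That the standard errors are certain to be too wide. At R2 = 0 they are not.
- That precision is lost. Stratified allocation already delivers it; it is under-reported.
- That the inflation is 3% to 12%. That is 1/sqrt(1 - R2) for all three factors at R2 of .05 to .20, and it ignores that sex is already named.
- That every planned contrast is affected. Treatment by time is not, with complete data and robust SEs. The plan expects only 70% retention through follow-up (about 45 of 64), and dropout was not simulated, so exact cancellation cannot be relied on.
- That adjustment helps abstinence. It widens the log-OR interval and moves the target to an odds ratio conditional on the added covariates, whereas the plan asks for population-averaged models.
- That the net error is towards caution. Unmodelled group clustering can push the other way by more, although that is a separate matter.
- That the arm-level means, percentages and SDs meant for planning are wrong. The argument concerns between-arm differences only.

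**Conclusion.** The point holds in limited form. Two of the three stratification factors are not pre-specified in the Aim 3 models. If they are prognostic, reported between-arm SEs for continuous outcomes would be about 2% to 8% wider than the adjusted SEs, equivalent to roughly 2 to 9 of the 64 participants. This rests on the assumed joint R2 of .05 to .20 in equal shares. Measured against the actual sampling SD, the simulated sex-only robust SE ranged from about 1% too small (R2 = .04) to 6% too large (R2 = .24), because uncorrected robust SEs run low at this sample size. The open covariate rule is a weakness at any R2. The change is worth making because it is cheap, but the consequence is modest: Aim 3 is descriptive, is declared underpowered, and feeds no feasibility benchmark.

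**What to change.** In section G, Aim 3, state that the between-arm GEEs for continuous outcomes include gender, race/ethnicity (non-Hispanic White vs Other) and smoking rate (20+ vs fewer than 20 cigarettes per day) as fixed main effects, and that any other covariate enters sensitivity analyses only.

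For 7-day abstinence, keep the population-averaged estimate as the main one, or fit the adjusted model and standardise it to a marginal effect. Say which is the target.

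State whether SEs are robust or model-based and, if robust, whether a small-sample correction is used. Without one, the adjusted robust SE in the simulation was somewhat too small (null rejection .062 to .077).

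The cost is a few sentences and two extra parameters at N = 64, with no new data, since both factors are already recorded for randomisation. The rule for modelling therapy group needs separate consideration and is not resolved by this change.

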Table 5. Measureable Benchmarks

Area of Interest	Description of Outcome to be Evaluated	Measure and/or Expected Outcome
Acceptability	Participant Satisfaction	Client Satisfaction Questionnaire ¹⁵⁸ (satisfaction of ≥80%)
	Intention to continue to use skills learned from the treatments	Questionnaire developed for this study
	Perceived appropriateness of the treatments for smoking and alcohol use	Questionnaire developed for this study
Demand	Accrual rates for study	For recruitment, the cost of each participant will be ≤\$100
	Completed sessions	≥40% of participants will complete all 8 sessions; ≥60% will complete between 4 and 7 sessions*
	Homework Completion	For MBRP-SA, participants will engage in mindfulness homework at a minimum of 3.5 days per week*
Implementation/ Practicality	Screening/eligibility for study	Record number of call attempts for each participant and reasons for ineligibility
	Recruitment	Recruit 8 eligible participants per month; 60% of recruitment will be completed by the end of year 2
	Retention	Retain 80% through end of treatment, 70% through follow-up
	Questionnaire completion	For sessions attended, 90% of questionnaires will be completed

Note. * based on data from Bowen et al., 2014; Vidrine et al., 2016; Witkiewitz et al., 2014^{64,66,107}

Aim 3.

The primary goal of Aim 3 is to collect and examine descriptive data on proximal variables associated with smoking abstinence and reduced drinking (e.g., negative affect, craving), as well as distal variables (smoking abstinence, heavy alcohol use) from Study 2. Aim 3 will be underpowered to test for any main effects of treatment on clinical outcomes. Nonetheless collecting these data will contribute to our assessment of feasibility and will provide guidance as we determine the sample size for a full-scale efficacy trial.

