Negative Affect/Depression/Stress/Anxiety Measures. Center for Epidemiological Studies Depression Scale (CESD) is a 20-item self-report questionnaire that assesses depressive symptoms experienced within the past week.¹⁶⁵ Distress Tolerance Scale (DTS) is a 15-item, Likert-scale self-report measure of an individual's perception of his/her own emotional distress tolerance.¹⁶⁶ Perceived Stress Scale (PSS) is a widely used self-report measure that assesses the degree to which participants find their lives to be stressful.¹⁶⁷ Positive and Negative Affect Scale (PANAS) is a 20-item self-report Likert-scale measure that assesses an individual's positive and negative affect at a given point in time.¹⁶⁸

Alcohol and Smoking Outcomes. Alcohol Use. The Timeline Followback (TLFB)¹⁷¹⁻¹⁷³ will be used to determine daily, recent alcohol use via retrospective self-report. A calendar is provided to participants, and they indicate any key events that occurred on certain dates to aid their memory. Participants then indicate how much alcohol they drank on each day. The TLFB has been widely used, evaluated, and has strong psychometric properties.¹⁷¹⁻¹⁷³ The TLFB will collect alcohol use from the past 4 weeks at the phone screen. The TLFB will be administered at each of the following visits and will ask participants to report their use since the last time they completed the TLFB: before visits 4 and 8, and at the 8-week and 16-week follow-up. From the TLFB, the primary outcome measure derived will be the percent of heavy drinking days (defined as: on a single occasion, ≥ 5 drinks for men and ≥ 4 drinks for women). Other alcohol use outcomes, such as percent days' abstinent and alcoholic drinks per drinking day, will also be derived.

Smoking Abstinence. To determine smoking abstinence, we will use the 7-day point prevalence, which is a combination of a self-report of no smoking in the last 7 days, combined with a biochemical verification of abstinence via saliva cotinine. Participants who report abstinence will be mailed a saliva cotinine kit to confirm abstinence at their 16-week follow-up call. The TLFB will be used to collect tobacco use throughout the study, and the schedule will mimic that used to collect alcohol use.

G. Data Management and Statistical Considerations for Study 2

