A similar approach to analysis will be taken for the primary outcomes (the distal measures). TLFB will be used to derive a measure of heavy alcohol use and the 7-day point prevalence will be created for smoking abstinence at five targeted 1-week periods prior to a session: start of treatment (week -4), quit date (week 0), end of treatment (week +3), and two follow-ups (week +8 and week +16). Descriptive statistics will be presented in figures. GEE with an AR(1) working correlation matrix ($r=.60$) will be used to assess the effects of treatment, time (-4, 0, +3, +8, +16), and their interaction on the primary outcome measures. Means, percentages, and 95% confidence intervals will provide useful guidance as we determine sample sizes for a full-scale RCT. There is not adequate power to detect small- to medium-sized treatment group differences given the sample size. However, we would interpret any within-subject decreases in the number of heavy drinking days from pre- to post-treatment and/or any within-subject increases in smoking abstinence as evidence that the MBRP-SA intervention may be beneficial for these two problematic health behaviors. Given the small sample size, these changes are not likely to be significant. However, sample means and standard deviations will provide valuable data for

estimating sample size in a large-scale RCT. Changes in craving, self-efficacy, and general use of alcohol and smoking will also be examined as proximal outcomes that will also inform the development of a large-scale trial.

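### Available-case GEE is the only provision for missing abstinence data; if smokers are lost more often, the percentages meant to size the full-scale trial will be too high

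*Combined protocol and SAP*

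**What the plan says.** All references are to the combined protocol and SAP, section 2, mainly part G (Data Management and Statistical Considerations for Study 2).

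- **Proximal measures (Aim 3 analysis):** "Generalized estimating equations (GEE) will be used to fit population-averaged models with the main variables of treatment, time, and their interaction". The one sentence on incomplete outcomes follows: "This approach preserves data for analysis by avoiding listwise deletion of observations when at least one dependent variable was observed". On adjustment: "Covariates and potential confounding variables will be included, as warranted". The data analysis overview adds sex as a covariate throughout.
- **Distal measures (heavy drinking and 7-day abstinence):** "A similar approach to analysis will be taken for the primary outcomes (the distal measures"). GEE with an AR(1) working correlation of .60 "will be used to assess the effects of treatment, time (-4, 0, +3, +8, +16), and their interaction on the primary outcome measures". Descriptive percentages with intervals are also to be shown and used in choosing the sample size of a full-scale trial. Any within-person rise in abstinence is to be read as a sign of possible benefit.
- **Retention:** Table 5 has "Retain 80% through end of treatment, 70% through follow-up"; the Aim 2 analysis text has "retain at least 80% through the end of treatment, and retain at least 70% through the end of the study".
- **Abstinence definition (Alcohol and Smoking Outcomes):** "a self-report of no smoking in the last 7 days, combined with a biochemical verification of abstinence via saliva cotinine". Kits are mailed for the 16-week call only.

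The plan gives no missing-data assumption, no rule for coding a participant who is not reached or a kit that is not returned, no weighting or imputation, and no sensitivity analysis. Section 4 only points back to the Aims.

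**The concern.** Avoiding listwise deletion describes which data are used. It does not say that those data represent everyone randomised. Unweighted GEE uses observed visits only. It is unbiased when loss is unrelated to outcome, or related only through covariates in the model. In a cessation trial it is plausible that people who relapse are harder to reach, and the plan does not address this.

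What is at stake is the declared product of Aim 3. The aim is descriptive and underpowered, so its use lies in the estimates. Abstinence rates that are too high would carry straight into the assumptions for the next trial, even if this study meets its own retention targets. Retention that differs between the arms could also produce a difference that is not real.

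**Working it through.** **Inputs from the documents.** N = 64 in balanced blocks of 4, so 32 per arm; retention of at least 80% and 70%; GEE with AR(1), r = .60; detectable effects d = .72 and OR = 5.95. The documents give no abstinence rate and no dropout pattern, so every such figure below is an assumption.

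**1. The plan's own figures.** At 32 per arm, two-sided α = .05, a t-test has power 0.809 at d = 0.72, and the detectable d at 80% power is 0.711. The stated figure is reproduced. For OR 5.95 the plan names no reference rate. At an assumed 10%, the odds are 0.111 × 5.95 = 0.661, a rate of 39.8%, which needs 32 per arm (power 0.802). Both figures take all 64 as followed. At 70% retention (22.4 per arm) the detectable d is 0.86. That is a loss of precision, separate from the bias examined here.

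**2. Loss the benchmarks allow.** 64 × 0.20 = 12.8 by end of treatment and 64 × 0.30 = 19.2 by follow-up.

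**3. Bounds for the raw percentage.** Let r be the proportion retained, p the abstinence rate among those observed, and f the abstinence rate among the lost divided by p. The whole-sample rate is rp + (1 − r)fp, so the observed rate is too high by the factor 1/[r + (1 − r)f].

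- r = 0.80: f = 0 gives 1/0.80 = 1.25; f = 0.5 gives 1/0.90 = 1.11; f = 1 gives 1.
- r = 0.70: f = 0 gives 1/0.70 = 1.43; f = 0.5 gives 1/0.85 = 1.18; f = 1 gives 1.
- In points at r = 0.70, for p from 10% to 40%: 3 to 12 if all the lost smoke (p × 0.30), 1.5 to 6 if they quit at half the rate (p × 0.15), and none if they quit at the same rate.

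**4. Raw percentage against the planned GEE.** Large-sample simulation of four visits with assumed true abstinence of about 45%, 35%, 28% and 22% and retention of about 100%, 80%, 75% and 70%. Under informative loss, smokers are four times as likely to drop out. The working correlation is fixed AR(1), r = .60. Results at the last visit:

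| Loss depends on | True | Raw observed | AR(1) GEE | Missing = smoking |
|---|---|---|---|---|
| Nothing (random) | 22.1% | 22.1% | 22.1% | 15.6% |
| Earlier, observed smoking | 21.9% | 25.7% | 23.0% | 17.9% |
| Current, unobserved smoking | 22.4% | 27.1% | 25.5% | 18.9% |

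Under informative loss the raw error is 25.7 − 21.9 = 3.8 and 27.1 − 22.4 = 4.7 points. The GEE error is 23.0 − 21.9 = 1.1 and 25.5 − 22.4 = 3.1 points. A second run under the same main assumptions gave 25–27% raw, 22–25% by GEE and 15–18% with missing counted as smoking. This gives the ranges of about 3 to 5 points (raw) and 0 to 3 points (GEE).

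**5. Arm contrast.** When loss depends on current status, observed odds = true odds × (retention of abstainers ÷ retention of smokers). If that ratio is the same in both arms it cancels from the odds ratio, and no false difference arises. It matters when the arms differ. Suppose 7 of 32 are abstinent in each arm, 26 and 19 are followed (45/64 = 70% overall), and all the lost smoke. The rates then read 7/26 = 27% and 7/19 = 37%. At those numbers the 95% interval on the difference is about ±28 points.

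**The case against.** Several points on the other side are fair, and most of them stand.

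- **A reader might infer that abstinence is overstated.** The documents do not support this as a fact: they report no abstinence rates and no reasons for dropout. At week 16 the error could run the other way if unreturned kits are counted as not abstinent.
- **A reader might infer that 20–30% loss is planned.** The figures are retention benchmarks, so they mark the most loss the plan would accept.
- **A reader might infer that the GEE is valid only under completely random loss.** It also holds when loss depends only on modelled covariates. When dropout followed observed smoking, AR(1) GEE was off by only about 1 point.
- **Missed participants need not drop out of the denominator.** The Timeline Followback asks about use since its last completion, on the same schedule for tobacco. Someone missed at +3 or +8 and reached later can therefore supply the missed week.
- **Counting missing as smoking is not a neutral replacement.** It was too low in every scenario, including random loss, where the available-case rate had no bias. It does not cure unequal retention either: with 20% true abstinence in both arms and random loss, 26/32 against 19/32 followed gives 16% against 12%.
- **Continuous outcomes are little affected.** A large-sample check put the AR(1) GEE bias at about 0.05 SD at week 16, too little to justify changing that analysis.
- **Study 2's primary outcomes are the Table 5 benchmarks,** and Aim 3 is descriptive.

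None of this supplies the missing rule. Reminder calls, collateral contacts, mailed materials and the early-dropout interview may reduce or explain loss, but they do not say how it is analysed. Low power does not excuse bias in estimates whose stated use is planning.

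**Conclusion.** The concern holds in conditional form. Available-case GEE, with raw percentages beside it, is the only handling of missing abstinence data, while the benchmarks tolerate up to 20% loss by end of treatment and 30% by follow-up. Random loss, or loss explained by modelled covariates, causes no bias. If smokers are lost more often, the raw percentages are too high by about 3 to 5 points and the AR(1) GEE estimates by about 0 to 3 points. These sizes rest on assumed 22% abstinence, about 70% retention and a fourfold dropout risk for smokers. The arm contrast is at risk only if loss, or its link to smoking, differs by arm, and nothing in the documents predicts that.

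The consequence is moderate. It does not touch the feasibility benchmarks, but it affects the rates meant to inform the full-scale trial. The remedy is a cheap improvement and does not require the analysis to be redesigned.

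**What to change.** Keep the GEE and add the following to part G before analysis:

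1. State the missing-data assumption under which the GEE estimates are to be read.
2. Report abstinence at +3, +8 and +16 for all 64 as randomised with missing counted as smoking, beside the available-case rate. Present the pair as a bracket, not as a new main analysis. It contains the true rate as long as smokers are lost at least as often as abstainers.
3. Add a multiple-imputation analysis using arm, baseline smoking rate and earlier smoking status.
4. Fill intermittently missed weeks from the later Timeline Followback where the participant is reached again.
5. For week 16, code self-reported abstainers whose cotinine kit is not returned both ways and show both results.
6. Tabulate dropout by arm and by last known smoking status.
7. Carry the resulting range, not a single rate, into planning of the full-scale trial.

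The cost is SAP wording and modest programming, with no new data collection. The drawback is that missing = smoking is biased low, so it should never be shown alone. The analysis of the continuous outcomes can stay as it is.
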